## 2 STATISTICAL AND ANALYTICAL PROCEDURES

### 2.1 ANALYSIS ENDPOINTS

#### 2.1.1 Demographic and baseline characteristics

The baseline value is defined as the latest available value before the first infusion in the original study except for hematology parameters and ECG parameters; the definition of baseline for these parameters could be found in [Section 2.6.1](#).

In addition to baseline parameters listed below, all baseline safety and efficacy parameters are presented along with the on-treatment summary statistics in the safety and efficacy sections ([Section 2.4.7](#) and [Section 2.4.8](#)).

##### *Demographic characteristics*

Demographic variables are: gender (Male, Female); race (White, Black, Asian, American Indian or Alaska Native, Native Hawaiian or other Pacific Island, Other, Not reported, Unknown); age in years prior to first olipudase infusion at original study; ethnicity (Hispanic, non-Hispanic), Ancestry (Arab, Jewish, Turkish, Mediterranean, Eastern European, Dutch, South American Native Indian, Other, Not reported, Unknown), sub-ancestry for Jewish (Askhenazi, Sephardic, Unspecified) and for Mediterranean (Moroccan, Tunisian, Algerian, Other). This data will be cross-checked against the original study and should match.

##### *Medical history*

Medical history at the time of entry into this extension study will be collected by body system regarding the presence or absence of any condition, and whether the condition is current or past. In addition, medical history of special interest, eg, pneumonia, bronchitis, etc, to ASMD will be collected regarding presence of any such history. Substance abuse (smoking and alcohol) data are also collected.

#### 2.1.2 Prior or concomitant medications

Medications are carried over from the original study when the medication is continuing at the time of the signing of informed consent or taken 30 days prior to the informed consent. Medications used before 30 days of signing of informed consent may be entered in the database at the discretion of the investigator.

Concomitant medications will continue to be collected throughout the study until the final visit of the study.

All medications will be coded using the World Health Organization-Drug Dictionary (WHO-DRUG) using the version in effect at Sanofi at the time of database lock.

All medications contained in the database of this study are considered concomitant medications since they are either continuing into or have started during this extension phase. During the study, certain antidepressants that may decrease olipudase alfa activity are prohibited; a detailed list is available in the study manual. This list is updated at least once a year with any change in WHO-DRUG versions. Cationic amphiphilic antihistamines, such as loratadine, desloratadine, astemizole, ebastine, terfenadine, and clemastine, may decrease olipudase alfa activity. Therefore, the need for their use in oral or IV administration should be carefully considered. For these medications, an exhaustive list cannot be provided, hence their use is left to the discretion of the investigator.

Due to scheduled liver biopsies in adult patients, certain medications and herbal supplements can be hepatotoxic or can cause or prolong bleeding, and should not be taken within 10 days before and 3 days after the biopsy procedure. Potentially hepatotoxic medications or herbal supplements include, but are not limited to, 3-hydroxy-3-methylglutaryl-coenzyme A reductase inhibitors, erythromycin, valproic acid, antidepressants, kava, and echinacea. Medications that may cause or prolong bleeding include, but are not limited to, anticoagulants, ibuprofen, aspirin, garlic supplements, ginkgo, and ginseng. For these two classes of medications, exhaustive lists cannot be provided, hence their use is left to the discretion of the investigator.

### **2.1.3 Safety endpoints**

The safety analysis will be based on the reported adverse events and other safety information, such as clinical laboratory data, vital signs, ECG, etc.

#### ***Observation period***

The observation period in this study is the **treatment epoch**, which is defined as from the first infusion of IMP (included) from the original study to the latest available date of data in the current study.

##### **2.1.3.1 Adverse events**

Adverse events are defined in the protocol, Section 10.5.1.1. All adverse events (including serious adverse events will be coded to a lower-level term (LLT), preferred term (PT), high-level term (HLT), high-level group term (HLGT), and associated primary system organ class (SOC) using the version of Medical Dictionary for Regulatory Activities (MedDRA) currently in effect at Sanofi at the time of database lock.

Adverse events are recorded from the time of informed consent until the end of study. Any AE that has been ongoing in the original study at the time of informed consent in this study will be copied over to this study's database and will be followed.

A serious adverse event (SAE) is any untoward medical occurrence that at any dose:

- Results in death, or
- Is life-threatening (**Note:** The term “life-threatening” in the definition of “serious” refers to an event in which the patient was at risk of death at the time of the event; it does not refer to an event which hypothetically might have caused death if it were more severe), or
- Requires inpatient hospitalization or prolongation of existing hospitalization, or
- Results in persistent or significant disability/incapacity, or
- Is a congenital anomaly/birth defect.
- Is a medically important event.

Adverse events of special interest (AESI) include:

Protocol-defined IAR: Any AE that occur during the infusion or within up to 24 h after the start of the infusion and is considered related or possibly related to study treatment as judged by the investigator or the sponsor is defined as a protocol-defined IAR. An event occurring  $\geq 24$  h after the start of an infusion may be judged an IAR at the discretion of the investigator or sponsor. Sponsor identification will reconcile with investigator identification of IAR before the database lock as much as possible. It is, however, possible that the sponsor identifies an AE as an IAR which the investigator did not agree to be an IAR.

Hypersensitivity IARs: A subset of protocol-defined IARs will also be defined programmatically by searching for preferred terms within Hypersensitivity SMQs (ie, SMQ code 20000214 Broad and Narrow scope).

Algorithm-defined IAR: All AEs that start between the start of infusion and the end of infusion plus 24 hours are defined as algorithm-defined IARs, irrespective of the perceived relation with study treatment. If an AE with missing time starts on the end of infusion date or on the following day, the AE will be considered an algorithm-defined IAR.

Pregnancy: Pregnancy of a female patient enrolled in the study as well as pregnancy occurring in female partner of a male patient enrolled in this study are captured as an AESI.

Symptomatic overdose: This is captured as an adverse event in this study. For details, please see Section 10.5.1.3.3 in the protocol.

Quantifiable Dose Limiting Toxicities (DLT) defined based on laboratory values: The following laboratory values and symptoms will be considered as Quantifiable Dose Limiting Toxicities:

- DLT1: Any increase in AST, ALT, total bilirubin, or AP  $>3x$  baseline (prior to olipudase alfa therapy) and  $>$  ULN.
- DLT2: Any increase in total bilirubin or AP  $>1.5x$  baseline in the presence of AST or ALT  $> 2x$  ULN.

- DLT3: Any increase in ALT or AST  $>3x$  the ULN combined with an increase in ALT or AST  $>2x$  baseline (prior to olipudase alfa therapy) with symptoms of fatigue, nausea, vomiting, right upper quadrant pain or tenderness, fever, rash, or eosinophilia ( $>$  ULN).

Adverse events of other interests include:

- Infections: TEAEs under the system organ class of Infections and Infestations
- Bleeding: TEAEs under the standard MedDRA queries (SMQs) of Hemorrhages (identified using SMQ code 20000038 broad and narrow scope).

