In a completed Phase 1 study (5), the safety, PK, and PD profiles of single, ascending doses of olipudase alfa were evaluated. Single doses of 0.03, 0.1, 0.3, 0.6, and 1.0 mg/kg of olipudase alfa were infused sequentially by dose cohort in 11 adult patients with ASMD. Study results found dose-related increases in ceramide, bilirubin, high-sensitivity C-reactive protein (hsCRP), and other acute phase reactants in patients that peaked 24 to 48 hours postdose and resolved by Day 14. Reported adverse events (AEs) involving constitutional symptoms (pain, fever, nausea, and vomiting) were consistent with first-dose-related toxicity and occurred in a dose-dependent fashion as was previously observed in the ASMKO mouse. Serious adverse events (SAEs) related to olipudase alfa treatment were not reported. The sponsor terminated the study subsequent to a single patient dosed at 1.0 mg/kg of olipudase alfa presenting with hyperbilirubinemia and an acute-phase reaction (APR) with clinical symptoms. Of note, this patient was subsequently confirmed to have Gilbert’s syndrome. Because there were no other signs of liver toxicity or hemolysis, the observed hyperbilirubinemia may have been secondary to specific inhibition of bilirubin uptake into hepatocytes and/or glucuronide conjugation of bilirubin within hepatocytes.

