8.1.5 Dosing delays or missed doses

Dose reintroduction regimens may be required for patients who have missed more than 1 dose between studies or during this study (LTS13632), depending on their usual dose. For patients receiving home infusions who have missed 2 or fewer doses, the investigator can decide whether reintroduction should occur at the hospital/study site via home infusion. For patients who have missed 3 or more doses ≥ 0.6 mg/kg, reintroduction of olipudase alfa should occur at the hospital/study site. If the site visit is not possible due to site closure or extenuating circumstances that prevent an in-person site visit (eg, during COVID-19 pandemic), reintroduction may be done via home infusion, if the patient has previously been approved for home infusion.

Patients who require dose reintroduction will have these assessments at each infusion until reaching their usual dose of olipudase alfa:

- Before infusion: vital sign measurements, liver function tests (LFTs), hematology tests and safety biomarkers.
- Immediately after infusion: vital sign measurements.
- 24 hours after infusion: vital sign measurements, LFTs, hematology and safety biomarkers
- 48 hours after infusion: vital sign measurements, LFTs and safety biomarkers.

The 48 hours post-infusion assessments will no longer be assessed after the cutoff date for a planned second database lock of the study for purpose of regulatory submissions in 2021.

During the dose escalation period, for transaminases assessed after infusion, if any AST or ALT value is $>2x$ baseline and $>ULN$, the test should be repeated prior to the next scheduled infusion. Depending on the test results, the dose can be adjusted (repeated or reduced) or treatment can be withheld to allow additional transaminase monitoring, based on the physician's clinical judgment.

Baseline is defined as the following:

- For initial dose escalation: last values prior to first dose of olipudase alfa
- For dose re-escalation: last values prior to the first re-escalation dose

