9.1.8 Vital sign measurements

Vital sign measurements will be obtained before and after infusions at the time points specified in the flow charts in [Section 1.1](#) through [Section 1.5](#). Patients must be in a supine position for approximately 5 to 10 minutes before their vital signs are measured. Vital sign measurements will include systolic and diastolic blood pressure (mm Hg), heart rate (beats/minute), respiratory rate (breaths/minute), and temperature (°F or °C).

For patients who have a dose reintroduction, vital signs will be measured at each visit before (within 30 minutes) the infusion, immediately after the infusion, and at 24 and 48 hours postinfusion until the patients are back on their usual dose of olipudase alfa ([Section 8.1.5](#)).

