Acute phase reactions are considered a type of IAR. Acute phase reactions were observed in the Phase 1 single-dose study (5) and the Phase 1b repeat-dose study (6) in 2 patients during dose escalation. The patients successfully completed the trial. Typically, APRs occurred within 12 to 72 hours after olipudase alfa infusion and were indicative of an inflammatory response as they were associated with elevations in hsCRP and changes acute phase reactants including, but not limited to, neutrophils, iron, ferritin, fibrinogen, D-dimer, transferrin, albumin, prothrombin time, and partial thromboplastin time. Typical AEs that were reported by the patient included, but were not limited to, pyrexia, nausea, vomiting, fatigue, and pain; and were concurrent with the changes in specific laboratory parameters. Accordingly, APRs will be determined based on combined significant laboratory findings and clinical symptoms.

10.5.1.3.2.3 Cytokine release syndrome

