10.5.2 Guidelines for reporting adverse events

10.5.2.1 General guidelines

See [Table 30](#) for an overview of AE reporting instructions.

- All AEs, regardless of seriousness or relationship to study treatment spanning from the signature of the informed consent form until the end of the study are to be recorded on the corresponding CRF.
- Except for IARs, whenever possible, diagnosis or single syndrome will be reported instead of symptoms. For IARs, all symptoms must be separately recorded.
- The investigator will specify the date of onset, intensity, action taken with respect to IMP, corrective treatment/therapy given, additional investigations performed, outcome, and his/her opinion as to whether there is a reasonable possibility that the AE was caused by the IMP.
- The investigator should take appropriate measures to follow all AEs until clinical recovery is complete and laboratory results have returned to normal, or until progression has been stabilized, or until death, in order to ensure the safety of the patients.
- Laboratory, vital sign measurements, or ECG abnormalities are to be recorded as AEs only if:
 - Symptomatic, and/or,
 - Requiring either corrective treatment or consultation, and/or,
 - Leading to IMP discontinuation or modification of dosing, and/or,
 - Fulfilling a seriousness criterion, and/or,
 - Defined as an AESI ([Section 10.5.1.3](#)).

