11.6.3.1.1 Adverse events of special interest

Detailed listings for AESIs, including IAR, APR, and CRS will be provided.

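### The SAP leaves out the acute phase reaction and cytokine release listings that the protocol requires, and its only causality-free reaction rule stops 24 hours after infusion

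*SAP*

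**What the plan says.** **Protocol.** Section 10.5.1.3 counts APRs and CRS, with hypersensitivity reactions, as kinds of IAR and so as adverse events of special interest (AESIs). Section 11.6.3.1.1 commits to an output: "Detailed listings for AESIs, including IAR, APR, and CRS will be provided". On timing, Section 10.5.1.3.2.2 states: "Typically, APRs occurred within 12 to 72 hours after olipudase alfa infusion". Sections 10.5.1.3.2.2 and 10.5.1.3.2.3 say that APR and CRS are each identified from laboratory findings and clinical symptoms taken together. Section 10.5.2.1 fixes how the data are entered: "For IARs, all symptoms must be separately recorded".

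**SAP.** Section 2.1.3.1 has two IAR rules.
- The protocol-defined IAR is automatic up to 24 hours from infusion start if the event is judged related or possibly related. An event at or beyond 24 "h after the start of an infusion may be judged an IAR at the discretion of the investigator or sponsor".
- The algorithm-defined IAR ignores relatedness: "All AEs that start between the start of infusion and the end of infusion plus 24 hours are defined as algorithm-defined IARs".

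Section 2.4.7.1.3 plans tables of protocol-defined IARs by time of onset, including more than 24 to 72 hours and more than 72 hours after infusion end. Section 2.4.7.1.6 repeats them by place of infusion. Hypersensitivity is the only IAR subtype with its own display. CRS appears once, in 2.1.3.3, as a reason to draw extra laboratory samples.

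**Assessments at reintroduction.** Protocol 8.1.5 says: "The 48 hours post-infusion assessments will no longer be assessed after the cutoff date". Protocol 9.1.8 still asks for vital signs "and at 24 and 48 hours postinfusion until the patients are back on their usual dose of olipudase alfa", with no cutoff date.

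**The concern.** Long-term safety is the primary objective, and APR and CRS are two of the reactions that the protocol singles out for it. A reader of the clinical study report would expect to learn how many patients had each. Under the SAP as written, no output answers that question.

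The second issue is the independence of the check. The algorithm-defined IAR does not depend on anyone's view of causality, so it can show whether judgement is missing reactions. It closes at 24 hours after infusion end, while the protocol's typical APR period runs to 72 hours. For most of that period the IAR tables hold only what an investigator or the sponsor chose to call an IAR, and nothing is planned to test that choice.

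**Working it through.** The plan states no figure on this point, so there is none to reproduce. The check sets passages side by side and then compares time windows.

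**1. Where APR and CRS appear**

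| Step | Protocol | SAP |
|---|---|---|
| Named as AESI | Yes (10.5.1.3) | Not in the AESI list (2.1.3.1) |
| Output | Listings (11.6.3.1.1) | None in AESI displays (2.4.7.1.3) |
| Narrative trigger | – | Only as part of protocol-defined IARs (2.5) |
| Departure declared | – | Not in 1.5, which declares only the treatment-period change |

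Document versions do not explain the gap. The SAP is based on Amended Protocol 4 and the protocol supplied is Amendment 07, but the change tables for Amendments 05, 06 and 07 list no change to 11.6.3.1.1.

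**2. Can the planned tables recover the syndromes?** No. Each symptom of an IAR is its own record and is tabulated by system organ class and preferred term. A patient with pyrexia, vomiting and raised hsCRP after one infusion contributes to separate rows, and laboratory markers are summarised elsewhere. Nothing links them to one reaction.

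**3. Are there such events in the data?** Protocol 10.5.1.3.2.2 reports APRs in the Phase 1b repeat-dose study, in 2 patients during dose escalation. That study is DFI13412, with 5 adults, all of whom went on to long-term treatment (Protocol 4.1; SAP 2.4). SAP 2.4.7 includes data from the prior study in the safety displays. Known APRs therefore fall within the analysis period without being identified as such.

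**4. Share of the APR period inside each rule.** The APR period is 72 − 12 = 60 hours. Protocol 10.5.1.3.2.2 does not say whether its clock starts at the beginning or end of the infusion, so both are shown. Infusion length L is not given in hours; 0.5 to 6 hours is assumed.
- Algorithm-defined IAR, clock from infusion end: (24 − 12)/60 = 12/60 = 20%.
- Algorithm-defined IAR, clock from infusion start: (12 + L)/60. For L = 0.5, 2, 4 and 6 this is 12.5/60 = 21%, 14/60 = 23%, 16/60 = 27% and 18/60 = 30%.
- Automatic part of the protocol-defined IAR: clock from end, (12 − L)/60, which is 19% at L = 0.5 and 10% at L = 6; clock from start, 12/60 = 20%.
- Protocol-defined IAR including the discretionary part: up to 100%, because it has no upper time limit.

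**5. What the later table holds.** With the clock from infusion end, the table for more than 24 to 72 hours spans 48/60 = 80% of the APR period. It contains only protocol-defined IARs, and every event in it is at or beyond 24 hours from infusion start. Entry is therefore by judgement alone.

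**6. Reintroduction.** Protocol 8.1.5 ends the 48-hour assessments, vital signs included, after the cutoff date. Protocol 9.1.8 keeps 48-hour vital signs and cross-refers to 8.1.5. The two cannot both be followed.

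**The case against.** The strongest reply is that nothing is lost. Every symptom is still a treatment-emergent event, tabulated by preferred term, severity and latest dose. IARs are reported to the sponsor within 24 hours, and Protocol 10.5.2.3.1 names APR and CRS there. The CRF asks whether an event is a manifestation of an IAR, and Table 30 provides a further specific form. SAP 1.6 says that narratives replace various listings, and 2.5 requires one for every protocol-defined IAR. SAP 2.4.7.1.1 also plans a listing of IARs that start in the extension.

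Much of this stands. It answers several stronger readings that a reader might infer:
- *That capture of reactions ends at 24 hours.* It does not. The protocol-defined IAR is open-ended and has tables beyond 24 and beyond 72 hours.
- *That CRS also falls at 12 to 72 hours.* The protocol gives that range for APR only. Section 10.5.1.3.2.3 has CRS symptoms developing soon after exposure.
- *That these events go largely uncounted, or that 70% to 80% are missed.* The events are counted; their identity as APR or CRS is not. The percentages are shares of a time window. The documents give no onset distribution, and the 12-to-72-hour range comes from earlier single-dose and dose-escalation studies, whereas patients enter this study at an established dose.
- *That ending assessments at 24 hours is itself an error, given Phase 1 markers including* "other acute phase reactants in patients that peaked 24 to 48 hours postdose". Amendment 06 made that change deliberately and gave a rationale. Whether it suffices is a clinical matter on which no view is taken here.

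The reply does not close the gap. SAP 1.6 does not say which listings are replaced, and 2.5 selects IARs without subtype. The documents supplied do not show that the extra CRF form records subtype. It is also fair that the protocol promises listings rather than counts, and that nothing obliges the algorithm-defined rule to reach 72 hours. Those two parts of the fix are recommendations; the listings are a commitment already made.

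**Conclusion.** The point holds in this form. The SAP omits, without declaring it, the APR and CRS listings in Protocol 11.6.3.1.1, and its remaining outputs cannot show which or how many patients had either reaction. That conclusion rests on the text alone. Separately, the one causality-free rule covers about 20% to 30% of the typical APR period: 20% with the clock from infusion end, and 21% to 30% from infusion start if infusions last 0.5 to 6 hours. Beyond 24 hours after infusion end, APRs enter the IAR tables only by investigator or sponsor judgement. This is a gap in identification and cross-checking; the documents do not show that events are lost. It should be fixed before database lock, since safety is the primary objective. The disagreement between Protocol 8.1.5 and 9.1.8 is real, but it is a matter of reconciling text.

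**What to change.** (a) In SAP 2.1.3.1 define APR and CRS as IAR subtypes, and in 2.4.7.1.3 add the listings that the protocol requires, with the number of patients and the number of infusions affected. This needs one clinical review before database lock that groups symptoms belonging to the same infusion. If narratives are meant to stand in for the listings, SAP 1.5 should say so and 2.5 should name the two subtypes; that would still give no counts.

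(b) Keep the algorithm-defined IAR as it is. Add a supplementary table, shown separately, of all adverse events starting more than 24 and up to 72 hours after infusion end, irrespective of causality, by system organ class and preferred term. Its drawback is that it will contain more unrelated events.

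(c) Reconcile Protocol 8.1.5 and 9.1.8 on 48-hour vital signs at reintroduction.

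The cost is SAP wording, the APR and CRS listing, two tables (the counts and the late-event table), the grouping review, and a wording change in the protocol. No new data collection is proposed.
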